9.8 Evaluation of Best Overall Response

Target Lesions	Non-Target Lesions	New Lesions	Overall Response
CR	CR	No	CR
CR	Non-CR/ Non-PD	No	PR
CR	Not evaluated	No	PR
PR	Non-PD/ or not all evaluated	No	PR
SD	Non-PD or not all evaluated	No	SD
Not all evaluated	Non-PD	No	Non-evaluable
PD	Any	Yes or No	PD
Any	PD*	Yes or No	PD
Any	Any	Yes	PD

*In exceptional circumstances, unequivocal progression in non-target lesions may be accepted as disease progression.

Subjects with a global deterioration of health status requiring discontinuation of treatment without objective evidence of disease progression at that time should be classified as having “symptomatic deterioration.” Every effort should be made to document the objective progression even after discontinuation of treatment.

In some circumstances, it may be difficult to distinguish residual disease from normal tissue. When the evaluation of complete response depends on this determination, it is recommended that the residual lesion be investigated (fine needle aspirate/biopsy) to confirm the complete response status.

9.9 Definitions for Response Evaluation – RECIST 1.1

9.9.1 First Documentation of Response

The time between initiation of therapy and first documentation of PR or CR.

9.9.2 Confirmation of Response

To be assigned a status of complete or partial response, changes in tumor measurements must be confirmed by repeat assessments performed no less than four weeks after the criteria for response are first met.

9.9.3 Duration of Response

Duration of overall response—the period measured from the time that measurement criteria are met for complete or partial response (whichever status is recorded first) until the date that recurrent or progressive disease is objectively documented (taking as reference for progressive disease the smallest measurements recorded since treatment started).

9.9.4 Duration of Overall Complete Response

The period measured from the time that measurement criteria are met for complete response until the first date that recurrent disease is objectively documented.

9.9.5 Objective Response Rate

The objective response rate is the proportion of all subjects with confirmed PR or CR according to RECIST 1.1, from the start of treatment until disease progression/recurrence (taking as reference for progressive disease the smallest measurements recorded since the start of treatment).

9.9.6 Clinical Benefit Rate

The proportion of patients with a confirmed complete response, a partial response or stable disease based on RECIST v1.1.

9.9.7 Progression-Free Survival

A measurement from the date of treatment initiation until the criteria for disease progression is met as defined by RECIST 1.1 or death occurs. Subjects who have not progressed will be right-censored at the date of the last disease evaluation.

9.9.8 Overall Survival

Overall survival is defined by the date of treatment initiation to date of death from any cause.

10 DRUG INFORMATION

10.1 Keytruda® (Pembrolizumab; MK-3475 [Anti-PD-1 Antibody MK-3475])

Please refer to the current version of the Investigator's Brochure (IB) for additional information regarding this drug.

10.1.1 Chemical name and properties

Humanized X PD-1_mAb (H409A11) IgG4

10.1.2 Availability

Pembrolizumab is commercially available and will be ordered through outpatient pharmacy where the subject is being treatment.

10.1.3 Storage

Clinical supplies must be stored in a secure, limited-access location under the storage conditions specified on the label. Receipt and dispensing of trial medication must be recorded by an authorized person at the trial site. Clinical supplies may not be used for any purpose other than that stated in the protocol.

10.1.4 Dosage and Administration

Pembrolizumab is a white to off-white lyophilized powder (50 mg/vial) or as a liquid solution (100 mg/vial) in Type I glass vials intended for single use only. Pembrolizumab Powder for Solution for Infusion, 50 mg/vial, is reconstituted with sterile water for injection prior to use. Pembrolizumab is formulated with L-histidine as buffering agent, polysorbate 80 as surfactant, sucrose as stabilizer/tonicity modifier, and hydrochloric acid (HCl) and/or sodium hydroxide (NaOH) for pH adjustment (if necessary). The drug product is stored as a stable lyophilized powder or liquid solution under refrigerated conditions (2°C - 8°C).

The product after reconstitution with sterile water for injection and the liquid drug product is a clear to opalescent solution, which may contain extraneous and proteinaceous particulates. The reconstituted product and liquid product is intended for IV administration. The reconstituted drug product solution and liquid drug product can be further diluted with normal saline in IV containers made of polyvinyl chloride (PVC) or non-PVC material. Reconstituted vials should be immediately used to prepare the infusion solution in the IV bag and the infusion solution should be immediately administered. If not used immediately, vials and/or IV bags may be stored at 2-8 °C for up to a cumulative time of 20 hours. If refrigerated, the vials and/or IV bags should be allowed to equilibrate to room temperature prior to subsequent use. Pembrolizumab solutions may be stored at room temperature for a cumulative time of up to 4 hours. This includes room temperature storage of reconstituted drug product solution and liquid drug product in vials, room temperature storage of infusion solution in the IV bag and the duration of infusion.

10.1.5 Side Effects

Please refer to the current version of the Investigator's Brochure for a complete list of adverse events.

Pembrolizumab is generally well tolerated and demonstrates a favorable safety profile in comparison to chemotherapy. Pembrolizumab is an immunomodulatory agent, and based on this mechanism of action, immune mediated adverse events are of primary concern. Important identified risks for pembrolizumab are of an immune mediated nature, including: pneumonitis, colitis, thyroid disorders (hypothyroidism/hyperthyroidism), hepatitis, hypophysitis, Type I diabetes mellitis, uveitis, nephritis, pancreatitis, myositis, and severe skin reaction. After a recent review of data, events newly characterized as identified risks also include vitiligo, Guillan-Barre Syndrome, and adrenal insufficiency. The majority of immune-mediated adverse events were mild to moderate in severity, were manageable with appropriate care, and rarely required discontinuation of therapy.

Further details around frequency, reporting, and management of immune-related adverse events (irAEs) can be found in the current version of the Investigator's Brochure. In addition to the previously noted identified risks, infusion-related reactions are a risk but are not considered immune mediated; these are also further described in the current IB.

10.2 Proleukin (Aldesleukin; Interleukin-2)

10.2.1 Chemical name and properties

Desalanyl-1, serine-125 human recombinant interleukin-2

MW: 15.3 KD

This IL-2 differs from native interleukin-2 in the following ways:

- Not glycosylated
- No N-terminal alanine
- C125S mutation
- Aggregation state

Biological potency: 1.1 mg = 18×10^6 IU

10.2.2 Availability

Proleukin is commercially available and will be ordered through outpatient pharmacy where the subject is being treatment.

10.2.3 Package

Sterile single-use vials intended for intravenous administration. Each vial contains 22×10^6 IU of lyophilized Proleukin.

10.2.4 Storage

Clinical supplies must be stored in a secure, limited-access location under the storage conditions specified on the label. Store vials of lyophilized Proleukin in a refrigerator at 2° to 8° C. Protect from light. Receipt and dispensing of trial medication must be recorded by an authorized person at the trial site. Clinical supplies may not be used for any purpose other than that stated in the protocol.

10.2.5 Dosage and Administration

Please refer to the Pharmacy Manual for a comprehensive description of Proleukin preparation. Reconstituted or diluted Proleukin is stable for up to 48 hours at 2° to 8° C.

Prometheus Laboratories will supply directly to sites at no cost to patients in this clinical trial. Proleukin is supplied as a sterile, white to off-white, lyophilized cake in single-use vials intended for intravenous administration. When reconstituted with 1.2 mL sterile water for injection, USP, each mL contains 18×10^6 IU (1.1 mg) Proleukin, 50 mg mannitol, and 0.18 mg sodium dodecyl sulfate, buffered with approximately 0.17 mg monobasic and 0.89 mg dibasic sodium phosphate to a pH of 7.5 (range 7.2 to 7.8). The manufacturing process for Proleukin involves fermentation in a defined medium containing tetracycline hydrochloride. The presence of the antibiotic is not detectable in the final product. Proleukin contains no preservatives in the final product.

The recommended Proleukin treatment regimen is administered in the inpatient setting on a monitored unit. Each course of treatment consists of two 5-day treatment cycles, the cycles separated by rest period for 9 days. In each cycle, 600,000 IU/kg (0.037 mg/kg) will be administered as a 15-minute intravenous infusion every 8 hours for up to 14 consecutive doses over 5 days.

10.2.6 Side Effects

Please refer to the current version of the Investigator's Brochure for a complete list of adverse events.

The following adverse events (Grades 1-4) were seen in $\geq 30\%$ of 525 patients (255 with metastatic renal cell cancer and 270 with metastatic melanoma) treated with Proleukin®: hypotension (71%), diarrhea (67%), oliguria (63%), chills (52%), vomiting (50%), dyspnea (43%), rash (42%), bilirubinemia (40%), thrombocytopenia (37%), nausea (35%), confusion (34%), and creatinine increase (33%). Due to the potential severe adverse events that might accompany Proleukin therapy at the recommended dosages, thorough clinical evaluation will be performed to exclude subjects that are contraindicated to Proleukin therapy and patients that have significant cardiac, pulmonary, renal, hepatic, or CNS impairment. Adverse events are frequent, often serious, and sometimes fatal. Further details around frequency, reporting, and management of immune-related adverse events (irAEs) can be found in the current version of the Investigator's Brochure. In addition to the previously noted identified risks, infusion-related reactions are a risk but are not considered immune mediated; these are also further described in the current IB.

11 ADVERSE EVENTS

The descriptions and grading scales found in the NCI CTCAE v4.03 will be utilized for AE assessment. A copy of the CTCAE v4.03 can be downloaded from the CTEP website at <http://ctep.cancer.gov>. All forms for AE/SAE recording and reporting can be found in the Study Procedure Manual or in the EDC system (Documents and Information Tab).

11.1 Definitions

11.1.1 Adverse Event (AE)

An AE is any untoward medical occurrence whether or not considered related to the study drug that appears to change in intensity during the course of the study. The following are examples of AEs:

- Unintended or unfavorable sign or symptom
- A disease temporally associated with participation in the protocol
- An intercurrent illness or injury that impairs the well-being of the subject

Abnormal laboratory values or diagnostic test results constitute AEs only if they induce clinical signs or symptoms or require treatment or further diagnostic tests

Hospitalization for elective surgery or routine clinical procedures that are not the result of an AE (e.g., surgical insertion of central line) should not be recorded as an AE.

Disease progression should not be recorded as an AE, unless it is attributable to the study regimen by the site investigator.

11.1.2 Serious Adverse Event (SAE)

A SAE is an adverse event that:

- Results in death. **NOTE:** Death due to disease progression should not be reported as a SAE, unless it is attributable by the site investigator to the study drug(s)
- Is life-threatening (defined as an event in which the subject was at risk of death at the time of the event; it does not refer to an event which hypothetically might have caused death if it were more severe)
- Requires inpatient hospitalization for >24 hours or prolongation of existing hospitalization. **NOTE:** Hospitalization for anticipated or protocol specified procedures such as administration of chemotherapy, central line insertion, metastasis interventional therapy, resection of primary tumor, or elective surgery, will not be considered serious adverse events.
- Results in persistent or significant disability/incapacity
- Is a congenital anomaly or birth defect
- Is an important medical event (defined as a medical event(s) that may not be immediately life-threatening or result in death or hospitalization but, based upon appropriate medical and scientific judgment, may jeopardize the subject or may require intervention (e.g., medical, surgical) to prevent one of the other serious outcomes listed in the definition above). Examples of such events include, but are not limited to, intensive treatment in an emergency room or at home for allergic bronchospasm; blood dyscrasias or convulsions not resulting in hospitalization; or the development of drug dependency or drug abuse.

11.1.3 Unexpected Adverse Event

For this study, an AE is considered unexpected when it varies in nature, intensity or frequency from information provided in the current IB, prescribing information or when it is not included in the informed consent document as a potential risk. Unexpected also refers to AEs that are mentioned in the IB as occurring with a class of drugs or are anticipated from the pharmacological properties of the drug, but are not specifically mentioned as occurring with the particular drug under investigation.

11.1.4 Relatedness

AEs will be categorized according to the likelihood that they are related to the study drug(s). Specifically, they will be categorized using the following terms:

Unrelated	Adverse Event is not related to the study drug(s)
Unlikely	Adverse Event is doubtfully related to the study drug(s)
Possible	Adverse Event may be related to the study drug(s)
Probable	Adverse Event is likely related to the study drug(s)
Definite	Adverse Event is clearly related to the study drug(s)

11.2 Reporting

11.2.1 Adverse Events

- AEs will be recorded from time of signed informed consent until 30 days after discontinuation of HD IL-2.
- AEs will be recorded regardless of whether or not they are considered related to the pembrolizumab or HD IL-2.
- All AEs will be recorded in the subject's medical record and on the appropriate study specific eCRF form within the EDC system.
- Asymptomatic laboratory abnormalities that do not require treatment will not be collected as adverse events.

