5.1 Pembrolizumab Administration

Subjects will receive 200 mg pembrolizumab every 3 weeks for two cycles. Cycle length is 21 days (i.e., 3 weeks). On the last day of Cycle 2 (+ 3 days), disease status will be assessed via imaging. Following the pembrolizumab treatment, HD IL-2 treatment will commence.

Correlative research analyses during pembrolizumab administration include examining the relationship between clinical response at the end of Cycle 2 with PD-L1 expression of the archived diagnostic tumor tissue. Research analyses also include examining the relationship between changes in soluble PD-L1 level and Type 1 T helper cell/Type 2 T helper cell (Th1/Th2) ratios during therapy (assessed after the 2nd dose) relative to baseline and characterization of intestinal microbiome to the best clinical response (RECIST 1.1 criteria) and to treatment outcome.

Drug	Dose	Route	Schedule	Cycle Length
Pembrolizumab	200 mg	Intravenously (IV) over 30 minutes	Day 1 of each cycle	3 weeks (21 days)

¹ A window of - 1 or + 2 days may be applied to all study visits to accommodate observed holidays, inclement weather, scheduling conflicts etc. Date and time of each drug administration should be clearly documented in subject's chart and electronic case report forms (eCRFs).

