5.2 HD IL-2 Administration

After completing the 2 cycles of pembrolizumab, High Dose Interleukin-2 (HD IL-2) will be administered. This will require a hospital stay of at least 5 days for each treatment cycle. Established guidelines will be followed for safely administering HD-IL-2 and managing toxicities from this treatment [31,32]. Two treatment cycles will be administered, Cycle 2 being separated from Cycle 1 by approximately 9 days after completion (assuming subject has recovered from Cycle 1 adequately to proceed with Cycle 2). Four weeks after completion of the 2 cycles (called a course of HD IL-2 therapy), disease status will be monitored via CT of the chest and abdomen/pelvis using revised RECIST guidelines (version v1.1, Section 9 of protocol).

Correlative research analyses in this phase include examining the relationship between changes in soluble PD-L1 level and Type 1 T helper cell/Type 2 T helper cell (Th1/Th2) ratios assessed after each of the two HD IL-2 cycles relative to baseline (i.e., pre-dose on Day 1 of Cycle 1 of pembrolizumab treatment), to the best clinical response (modified RECIST criteria) and to treatment outcome.

Drug	Dose	Route	Schedule	Cycle Length
IL-2	600,000 IU/kg ²	Intravenously (IV) over 15 minutes	Every 8 hours for up to 14 doses over 5 days	Days 1-5 = Cycle 1 9 days of rest in between Days 15-19 = Cycle 2

¹ A window of - 1 or + 2 days may be applied to all study visits to accommodate observed holidays, inclement weather, scheduling conflicts etc. Date and time of each drug administration should be clearly documented in subject's chart and electronic case report forms (eCRFs).

²Actual weight will be used unless the patient is 30% over ideal body weight in which case adjusted body weight will be used (Males: IBW = 50 kg + 2.3 kg for each inch over 5 feet.

Females: IBW = 45.5 kg + 2.3 kg for each inch over 5 feet); ABW = IBW + 0.4(actual weight - IBW)

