5.3.1 Allowed Concomitant Medications

All treatments that the investigator considers necessary for a subject's welfare may be administered at the discretion of the investigator in keeping with the community standards of medical care. All concomitant medications will be recorded on the electronic case report form (eCRF).

All concomitant medications received within 28 days before the first dose of trial treatment and 30 days after the last dose of trial treatment should be recorded. Concomitant medications administered beyond 30 days after the last dose of trial treatment should be recorded for SAEs and ECIs.

Myeloid growth factors to treat subjects with neutropenia according to the American Society of Clinical Oncology (ASCO) Guidelines are permitted. Myeloid growth factors should be avoided (if medically appropriate) in Cycle 1 until subjects have developed a dose-limiting Grade 4 neutropenia.

Antiemetic agents may be administered at the discretion of the site investigator but are not commonly required as a prophylactic agent. All other manifestations of the subject's malignancy should be treated at the discretion of the investigator.

Medications with potential central nervous system (CNS) effects are not prohibited in this study, but it is recommended that their use be minimized to avoid confusion in the interpretation of CNS effects should they occur during the course of treatment with pembrolizumab.

In appropriate settings, such as combinations with agents known to produce frequent thrombocytopenia, restricted uses of anticoagulants should be considered.

All other medical conditions should be treated at the discretion of the site investigator in accordance with local community standards of medical care.

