5.5 Use in Pregnancy

If a subject inadvertently becomes pregnant while on study treatment, the subject will immediately be removed from the study. The site will contact the subject at least monthly and document the subject's status until the pregnancy has been completed or terminated. The outcome of the pregnancy will be reported to Hoosier Cancer Research Network (HCRN) **within 1 business day** if the outcome is a serious adverse experience (e.g., death, abortion, congenital anomaly, or other disabling or life-threatening complication to the mother or newborn). HCRN will report this information **within 1 business day** to Prometheus. The study investigator will make every effort to obtain permission to follow the outcome of the pregnancy and report the

condition of the fetus or newborn to HCRN. If a male subject impregnates his female partner, he must immediately inform the site study personnel and the pregnancy reported and followed as described above.

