6.1.3 Dose Modification for Toxicity

Adverse events (both non-serious and serious) associated with pembrolizumab exposure may represent an immunologic etiology. These adverse events may occur shortly after the first dose or several months after the last dose of treatment. Pembrolizumab must be withheld for drug-related toxicities and severe or life-threatening AEs as per Table 2 below.

Table 2: Dose Modification and Toxicity Management Guidelines for Immune-related AEs Associated with Pembrolizumab

General instructions:				
Immune-related AEs	Toxicity grade or conditions (CTCAEv4.0)	Action taken to pembrolizumab	irAE management with corticosteroid and/or other therapies	Monitor and follow-up
Pneumonitis	Grade 2	Withhold	
 Administer corticosteroids (initial dose of 1-2 mg/kg prednisone or equivalent) followed by taper 	
 Monitor participants for signs and symptoms of pneumonitis Evaluate participants with suspected pneumonitis with radiographic imaging and initiate corticosteroid treatment Add prophylactic antibiotics for opportunistic infections
	Grade 3 or 4, or recurrent Grade 2	Permanently discontinue		
Diarrhea / Colitis	Grade 2 or 3	Withhold	
 Administer corticosteroids (initial dose of 1-2 mg/kg prednisone or equivalent) followed by taper 	
 Monitor participants for signs and symptoms of enterocolitis (ie, diarrhea, abdominal pain, blood or mucus in stool with or without fever) and of bowel perforation (ie, peritoneal signs and ileus). Participants with \geq Grade 2 diarrhea suspecting colitis should consider GI consultation and performing endoscopy to rule out colitis. Participants with diarrhea/colitis should be advised to drink liberal quantities of clear fluids. If sufficient oral fluid intake is not feasible, fluid and electrolytes should be substituted via IV infusion.
	Grade 4	Permanently discontinue		

AST / ALT elevation or Increased bilirubin	Grade 2	Withhold	
 Administer corticosteroids (initial dose of 0.5- 1 mg/kg prednisone or equivalent) followed by taper 	
 Monitor with liver function tests (consider weekly or more frequently until liver enzyme value returned to baseline or is stable)

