- 11: The safety follow-up visit should occur when subjects permanently stop study treatment for whatever reasons (toxicity, progression, or at discretion of site investigator) and should be performed 30 days (± 7 days) after the last dose of treatment. Subjects who have an ongoing Grade \geq 2 or serious AE (SAE) at this visit will continue to be followed until the AE resolves to \leq Grade 1 or baseline, deemed clinically insignificant, and/or until a new anti-cancer treatment starts, whichever is earlier.
- 12: Long-term follow up will occur in all subjects after the safety follow up visit. Subjects who discontinue treatment for any reason will be followed every 3 months for 12 months. Follow up may be accomplished via clinic visit, phone call, or other avenues as appropriate.

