11.2.2 Serious Adverse Events (SAEs)

11.2.2.1 Site Requirements for Reporting SAEs to HCRN

- SAEs will be reported from time of signed informed consent until 30 days after discontinuation of HD IL-2.
- SAEs will be reported on the SAE Submission Form **within 1 business day** of discovery of the event.
- SAEs include events related and unrelated to pembrolizumab or HD IL-2.
- All SAEs will be recorded in the subject's medical record and on the appropriate study specific eCRF form within the EDC system.

The site will submit the completed SAE Submission Form to HCRN **within 1 business day** of discovery of the event. The form may be submitted to HCRN electronically to [contact]. The site investigator is responsible for informing the IRB and/or other local regulatory bodies as per local requirements.

The original copy of the SAE Submission Form and the email correspondence must be kept within the study file at the study site.

Once the SAE has resolved (see resolution guidelines listed above), sites must submit a follow-up SAE Submission Form within a reasonable timeframe to HCRN electronically to [contact].

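### AE and SAE capture closes 30 days after HD IL-2, short of the late-onset period the protocol itself describes, and the rule sets no end date for subjects who never start IL-2

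*Combined protocol and SAP*

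**What the plan says.** - Section 11.2.1: "AEs will be recorded from time of signed informed consent until 30 days after discontinuation of HD IL-2". Section 11.2.2.1 uses the same end point: "SAEs will be reported from time of signed informed consent until 30 days after discontinuation of HD IL-2".
- Section 6.1.3, on events associated with pembrolizumab exposure: "These adverse events may occur shortly after the first dose or several months after the last dose of treatment".
- Section 7, study calendar: AEs are listed up to and including the safety follow-up visit. The long-term column lists only survival status and subsequent therapy.
- Section 7, footnote 11: every subject who stops treatment, for any reason, has a safety visit 30 days (± 7) after the last dose of treatment. The calendar's column header gives 28 days (± 7). An ongoing SAE or Grade 2 or higher AE is followed until it returns to Grade 1 or baseline, is "deemed clinically insignificant, and/or until a new anti-cancer treatment starts, whichever is earlier".
- Section 7, footnote 12: follow-up is 3-monthly for 12 months. Section 12.1 ends scans and survival follow-up one year after the first pembrolizumab dose.
- Section 12.2.2: the safety endpoint is the proportion of subjects at each CTCAE grade, with 95% confidence intervals. Section 12.4 puts anyone who received a dose of study drug in the safety population.
- Section 5.5: "If a subject inadvertently becomes pregnant while on study treatment, the subject will immediately be removed from the study". Section 5.4 requires contraception for 120 days after the last dose.

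**The concern.** The protocol names a late-onset class of event and then closes its collection windows without providing for it. Sites remain in contact with subjects after the windows close but are not asked about toxicity at those contacts.

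The window is also tied to one drug of a two-drug sequence. Subjects who never reach IL-2 are foreseeable: a scan precedes IL-2, and documented progression ends protocol therapy, as do toxicity, investigator decision and subject request. These subjects count in the safety population, but neither reporting rule says when their capture ends.

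Characterizing the safety of this sequence is a secondary objective. If late immune events occur and are not recorded, the grade proportions omit them. Those proportions would also combine subjects observed for quite different periods after pembrolizumab. With at most 29 subjects, a single unrecorded event is visible in the result.

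**Working it through.** The plan gives no figure of its own here, so the check is calendar arithmetic.

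**Inputs.** Section 5.1: "Subjects will receive 200 mg pembrolizumab every 3 weeks for two cycles", with 21-day cycles. Section 5.2: the IL-2 course runs over Days 1-5 and then "Days 15-19 = Cycle 2". Sections 11.2.1 and 11.2.2.1: 30 days. Section 7: safety visit at 28 ± 7 or 30 ± 7 days.

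**Assumptions.** Day 1 is the first pembrolizumab dose, there are no delays, and IL-2 starts the day after pembrolizumab Cycle 2 ends.

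1. Second pembrolizumab dose: 1 + 21 = Day 22. Cycle 2 ends on 22 + 20 = Day 42.
2. IL-2 starts on Day 43. Its last dosing day is 43 + 18 = Day 61.
3. The window closes on 61 + 30 = Day 91, which is 91 − 22 = 69 days after the last pembrolizumab dose.
4. With a 3-day lag before IL-2: start Day 46, last dose Day 64, closure Day 94, and 94 − 22 = 72 days.
5. With one IL-2 cycle only: last dose 43 + 4 = Day 47, closure Day 77, and 77 − 22 = 55 days.
6. With two pembrolizumab doses and no IL-2, the rule gives no date. The safety visit falls on 22 + (28 ± 7) = Days 43 to 57, or 22 + (30 ± 7) = Days 45 to 59. That is 21 to 37 days after the last dose.

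| Course received | Last AE capture | Days after last pembrolizumab dose |
|---|---|---|
| Both drugs, complete | Day 91 | 69 |
| One IL-2 cycle | Day 77 | 55 |
| Two pembrolizumab doses only | Visit on Days 43 to 59; no date in the rule | 21 to 37 |

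For a completer, 365 − 91 = 274 of the first 365 days (75%) fall after closure.

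**What one unrecorded event would do.** Assume 29 subjects in the safety population and exact intervals; Section 12.2.2 does not name the method for AE proportions. For 0/29, the upper 95% limit is 1 − 0.025^(1/29) = 11.9%. For 1/29, the upper limit solves (1 − p)^29 + 29p(1 − p)^28 = 0.025, which gives 17.8%.

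**The case against.** The best defence is footnote 11. It gives every subject who stops a safety visit about 30 days after the last dose of any treatment, and the calendar lists AEs at that visit. A reader might infer that pembrolizumab-only subjects have no end to capture in practice, or no capture at all. The documents support neither. Read literally, the Section 11 rule never closes for them, which is not under-capture in itself. What stands is narrower: footnote 11 sets a visit, not a reporting window, so the rule remains undefined for these subjects.

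Other stronger readings also fail.

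- Taking 30 days as the whole of post-pembrolizumab capture would suggest that 60 of an assumed 90 days are lost. Section 6.1.3 speaks of pembrolizumab, and completers have 69 days, so the loss on that assumption is 90 − 69 = 21 days. The protocol puts no number on the late-onset period.
- The new-therapy cut-off might be thought to make the toxicity profile look benign. The event has already been recorded and graded by then. What is lost is its outcome and any later worsening of grade, and no direction of bias is shown.
- Section 5.3.1 says "Concomitant medications administered beyond 30 days after the last dose of trial treatment should be recorded for SAEs and ECIs". That can refer to SAEs that began inside the window and are still ongoing, so it does not prove that new late SAEs were meant to be collected.
- Section 11.2.2.1 refers back to resolution guidelines. Footnote 11 can serve as these, so they are not shown to be missing.
- Section 5.5 does not leave every pregnancy after treatment uncovered: its sentence on partners of male subjects has no time limit.
- Footnote 12 alone suggests 12 further months of contact. Section 12.1 may end it 274 days, about nine months, after Day 91.

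The Study Procedures Manual and the DSMB Charter are not available and could add instructions. Window length is also a design choice. Neither point reconciles Section 6.1.3 with Section 11.

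**Conclusion.** The concern holds in limited form. As written, the plan does not collect immune events that begin after about Day 91 in completers. For subjects who never start IL-2 it schedules no AE check later than 21 to 37 days after the last dose and states no reporting end date. Late events would be absent from the secondary safety endpoint, and capture after the last pembrolizumab dose would range from about 21 to 72 days within one denominator.

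These figures assume treatment on schedule; a delay before or during IL-2 lengthens the interval after pembrolizumab. How many events would be missed cannot be estimated from the documents. The response analysis, the two-stage rule and the sample size are untouched. This is an inexpensive improvement to safety ascertainment.

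**What to change.** 1. In Sections 11.2.1 and 11.2.2.1, run both windows from the last dose of either study drug, in line with footnote 11. Reconcile the 28-day and 30-day timings of the safety visit at the same time.
2. Keep 30 days for other AEs. Add SAEs and Table 2 immune-related events to the follow-up contacts already scheduled, with a flag for onset after new anti-cancer therapy. Re-anchoring alone supplies the missing end date but does not capture late onset, so both changes are needed.
3. In footnote 11, continue recording the outcome of ongoing SAEs after new therapy starts, with the same flag.
4. Reconcile footnote 12 with Section 12.1 on when follow-up ends.
5. Reconcile Section 5.5, which is limited to pregnancy during treatment, with the 120-day contraception period.

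The cost is a protocol amendment, a small eCRF addition, and more SAE work: one-business-day reports, relatedness review and follow-up forms. Some late events will be confounded by later therapy, which is the reason for the flag. Footnote 12 allows contact by phone, so some reports may need confirmation from medical records. No treatment rule changes.
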